Objectives	
The purpose of this study is to evaluate the safety and performance of the Nerivio Migra Migraine device for the treatment of non-chronic migraine patients with and without aura

Primary Endpoint	
Primary Performance Endpoint. Proportion (%) of patients reporting freedom from pain (pain grade 0) 2 hours post treatment without rescue medications in at least 50% of treated attacks
 
Primary Safety Endpoint. Device related adverse effects

Secondary & Exploratory Endpoints	
Performance endpoints:
 
Secondary:
 
 1. The proportion (%) of subjects reporting treatment response at 2 hours post treatment without medications in at least 50% of treated attacks. Treatment response is defined as pain level reduction from moderate or severe at baseline to mild or pain level of none if treatment started with mild pain. 2. Proportion (%) of patients reporting, 2 hours post treatment: 
 ▪ freedom from pain (pain grade 0) and their most bothersome migraine-associated symptom (MBS) in at least 50% of treated attacks ▪ freedom from nausea in at least 50% of treated attacks

	
 ▪ freedom from photophobia in at least 50% of treated attacks ▪ freedom from phonophobia in at least 50% of treated attacks 
Exploratory:
 
 3. The proportion (%) of patients reporting freedom from pain (pain grade 0) 48 hours post treatment without medications in at least 50% of treated attacks 4. The percent of subjects who are pain-free at 2 hours with no use of rescue medication, and either have no relapse of pain within the subsequent 46 hours, or, if they have a relapse of pain in this time window, it disappears every time, after two hours, using the device, with no use of rescue medications. 5. Patient global impression of change, with emphasis on disability and quality of life.
Safety Endpoints	
 • Treatment tolerability • Adverse events and complications whether related or unrelated to study device.
Patient Population	Adults 18-75 years old meeting International Headache Society criteria for migraine with and without aura, who are reporting 2-8 migraine attacks per month.
Number of Patients	Up to 248 patients with evaluable data, equally distributed between US and non-US sites

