6.3.2 Secondary Endpoints

Secondary Performance Endpoints

1. The proportion (%) of subjects reporting treatment response at 2 hours post treatment without rescue medications in at least 50% of treated attacks. Treatment response is defined as: pain level reduction from moderate or severe at baseline to mild or pain level of none if treatment started with mild pain
2. Proportion (%) of patients reporting, 2 hours post treatment:
 - freedom from pain (pain grade 0) and their most bothersome migraine-associated symptom (MBS) in at least 50% of treated attacks
 - freedom from nausea in at least 50% of treated attacks
 - freedom from photophobia in at least 50% of treated attacks
 - freedom from phonophobia in at least 50% of treated attacks

6.3.3 Exploratory Endpoints:

1. The proportion (%) of patients reporting freedom from pain (pain grade 0) 48 hours post treatment without medications in at least 50% of treated attacks

2. The percent of subjects who are pain-free at 2 hours with no use of rescue medication, and either have no relapse of pain within the subsequent 46 hours, or, if they have a relapse of pain in this time window, it disappears every time, after two hours, using the device, with no use of rescue medications.
3. Patient global impression of change, with emphasis on disability and quality of life.

6.3.4 Safety Endpoints:

- Treatment tolerability
- Adverse events and complications whether related or unrelated to study device.

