6.4.2.1 Start attack/episode PRO feedback data

The screen provides for collection of the following data:

Item	Description	Control type	Values range
Current migraine pain level	Current migraine pain level in pain grade categories	Dropdown list	Mild (1), Moderate (2), Severe (3).

Time from onset of migraine pain	Time from onset of migraine pain	Dropdown list	under 10 minutes 10-20 minutes 20-60 minutes 1-2 hours 2-4 hours over 4 hours
Nausea	Presence of nausea	Radio buttons	Y/N
Sensitivity to light	Presence of photophobia	Radio buttons	Y/N
Sensitivity to sound	Presence of phonophobia	Radio buttons	Y/N
Increased skin sensation	Presence of allodynia	Radio buttons	Y/N

6.4.2.2 2h PRO

This feedback dialog appears 2h after the treatment program has started.

The screen provides for collection of the following data:

Item	Description	Control type	Values range
Current migraine pain level	Current migraine pain level in pain grade categories	Dropdown list	No pain (0), Mild (1), Moderate (2), Severe (3).
Medication	Whether rescue medication was taken	Radio buttons	Y/N
Medication name	Rescue medication	Dropdown list	From a pre-defined list
Nausea	Presence of nausea	Radio buttons	Y/N
Sensitivity to light	Presence of photophobia	Radio buttons	Y/N
Sensitivity to sound	Presence of phonophobia	Radio buttons	Y/N

Increased skin sensation	Presence of allodynia	Radio buttons	Y/N
Arm side where device was applied	Left or right arm	Radio buttons	L/R
Pain location (side)		Dropdown list	L R both
Additional feedback	Additional, free style feedback	Textbox	Free text, optional

6.4.2.3 48h PRO

The screen shall provide for collection of the following data:

Item	Description	Control type	Values range
Current migraine pain level	Current migraine pain level in pain grade categories	Dropdown list	No pain (0), Mild (1), Moderate (2), Severe (3).
Medication	Whether rescue medication was taken	Radio buttons	Y/N
Medication name	Rescue medication	Dropdown list	From a pre-defined list
Additional feedback	Additional, free style feedback	Textbox	Free text, optional

6.4.3 *Methods and Timing of Assessing, Recording and Analyzing Variables*

Once the last patient will have completed the study and all the queries have been resolved, database will be locked, cleaned and exported for final statistical analysis. Study report will be issued following final database lock.

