7 STATISTICAL CONSIDERATIONS

7.1 *Study Design and Aim*

The study is designed as a prospective, randomized, double-blind, sham controlled multi-center clinical trial. The study aim is to demonstrate safety and effectiveness of Nerivio Migra electro stimulation device for treatment of migraine attacks with and without aura.

7.2 *Study Variables*

7.2.1 *Primary performance variable*

The primary performance endpoint, the proportion (%) of patients reporting freedom from pain (pain grade 0) 2 hours post treatment without rescue medications in at least 50% of treated attacks, will be measured in the form of a binary variable which will be assigned the value of "1" if the subject reports freedom from pain (pain grade 0) 2 hours post treatment without rescue medications in at least 50% of his/her treated attacks, and "0" otherwise.

7.2.2 *Secondary performance variables*

The secondary performance endpoints will all be expressed in the form of binary variables as in the representation of the primary performance variable.

7.2.3 *Exploratory performance variables*

The exploratory performance endpoint, the proportion (%) of patients reporting freedom from pain (pain grade 0) 48 hours post treatment without rescue medications in at least 50% of treated attacks, will be measured in the form of a binary variable which will be assigned the value of "1"

if the subject reports freedom from pain (pain grade 0) 48 hours post treatment without rescue medications in at least 50% of his/her treated attacks, and “0” otherwise.

Patient global impression of change is measured via a questionnaire.

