The numbers of patients who entered the study and completed each stage of the study will be provided per month, as well as the reasons for all post randomization discontinuations, grouped by major reason, e.g., lost to follow-up, adverse event, poor compliance, did not administer any treatment (with reasons). A list of discontinued patients, protocol deviations, and patients excluded from the performance analysis will be provided as well.

7.8.5 *Performance Analyses*

Primary Performance Analyses:

The primary endpoint is freedom from pain at 2 hours post treatment without rescue medications in at least 50% of treated attacks, a count and percentage of subjects free from pain will be calculated and presented for both study groups each with a two-sided 95% exact confidence interval. The groups will be compared with a chi-squared test.

If the null hypothesis is rejected in favor of the alternative hypothesis and the proportion (%) of subjects reporting freedom from pain at 2 hours post treatment without rescue medications in the treated group is greater than that of the sham group, the study will be deemed successful.

The primary endpoint will also be evaluated stratified by center using a Mantel-Haenszel test to assess the center by group interaction.

A sensitivity analysis of the primary end-point will be performed to assess the impact of missing data on the study outcome. This will be performed using several possible imputation methods.

Subset analysis:

Adjustment for other covariates such as demographics or other baseline patient characteristics may be performed by adding these variables into a logistic regression model.

Subgroup analysis according to use of preventive medications will be performed and reported by adding these variables to a logistic regression model.

Secondary performance analyses:

The secondary performance variables will be summarized by a count and percentage and compared with a chi-squared test.

Exploratory performance analyses:

A count and percentage of patients reporting freedom from pain (pain grade 0) 48 hours post treatment without rescue medications in at least 50% of treated attacks will be presented, the groups will be compared with a chi-squared test.

Use of rescue medications will be summarized by descriptive statistics per treatment group and compared between the groups with a t-test.

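### The nausea, photophobia and phonophobia endpoints count attacks that lacked the symptom at treatment start, so they mix absence, prevention and resolution and dilute any effect on resolution

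*Combined protocol and SAP*

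**What the plan says.** Section 6.3.2, item 2, and the synopsis define the three symptom endpoints over all treated attacks, assessed 2 hours after treatment: "freedom from nausea in at least 50% of treated attacks", "freedom from photophobia in at least 50% of treated attacks" and "freedom from phonophobia in at least 50% of treated attacks".

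Section 7.2.2 adds only the coding: "The secondary performance endpoints will all be expressed in the form of binary variables as in the representation of the primary performance variable". Section 7.8.5 adds only the test: "The secondary performance variables will be summarized by a count and percentage and compared with a chi-squared test". Neither these sections nor the analysis sets (7.7) or the missing-data section (7.8.7) makes the count depend on the symptom being present at the start.

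The information is collected. The start-of-attack screen (6.4.2.1) has yes/no items for "Presence of nausea" and "Presence of photophobia", and one for phonophobia. The 2-hour screen (6.4.2.2) repeats all three.

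Pain is handled differently. The start screen offers only mild, moderate or severe, so freedom from pain always means that existing pain went away. Secondary endpoint 1 also sets its success rule by the starting grade: "pain level reduction from moderate or severe at baseline to mild or pain level of none if treatment started with mild pain".

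**The concern.** Eligibility is decided per patient (6.5.1), and a qualifying attack is defined only by the preceding 48 headache-free hours (6.1). A treated attack need not include nausea, photophobia or phonophobia. Patients are told to treat at onset, and the shortest onset-to-treatment category on the start screen is under 10 minutes. A 'no' for a symptom at the start is therefore an expected answer.

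Under the wording as it stands, a subject who never has nausea is a nausea responder in either arm. The reported percentage then combines three things:

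- attacks that never had the symptom;
- attacks in which it was prevented;
- attacks in which it cleared.

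A reader will tend to take the figure as clearing. Attacks that never had the symptom add equally to both arms, which shrinks the contrast in resolution and costs power. These are formal secondary endpoints, tested once the primary succeeds (7.8.2.2).

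**Working it through.** **The plan's own figure.** Section 7.4 plans 10% versus 30% responders on the primary endpoint, with 80% power and two-sided 5%. The pooled chi-squared formula without continuity correction gives 61.6, so 62 per arm and 124 in total, with power 80.3%. The stated figure reproduces. No power is stated for the symptom endpoints, so I use 62 per arm for them.

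**Inputs from the plan.** Up to four attacks per subject (6.1), success in at least half of them (6.3.2), 1:1 allocation, two-sided 5%.

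**Assumptions, because the documents give no figures.** Let q be the share of attacks with the symptom at start, and s the chance that a present symptom clears by 2 hours (30% sham, 50% active). Attacks are independent, subjects do not differ, and no symptom newly appears by 2 hours.

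**As written.** Per-attack success is x = (1 − q) + q·s. The subject is a responder with probability P(Bin(4, x) ≥ 2).

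*Example, q = 0.5:* x = 0.5 + 0.5 × 0.3 = 0.65 (sham) and 0.5 + 0.5 × 0.5 = 0.75 (active). Responders are 87.4% and 94.9%. The per-attack difference is 20 × q = 10 points.

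**Restricted to attacks with the symptom at start.** The number of such attacks is k ~ Bin(4, q). Subjects with k = 0 drop out. The responder rate is the average over k ≥ 1 of P(at least half of k clear). Contributing subjects per arm are 62 × [1 − (1 − q)⁴].

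*Example, q = 0.5, sham:* the weights for k = 1 to 4 are 4, 6, 4 and 1 out of 15. The success probabilities are 0.300, 0.510, 0.216 and 0.348. The result is 36.5%. Active gives 61.3%, and 62 × 15/16 = 58 subjects per arm contribute.

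**Power** = Φ{[Δ√n − 1.96·√(2p̄(1 − p̄))] / √[p₁(1 − p₁) + p₂(1 − p₂)]}.

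| Prevalence at start | As written, sham vs active | Power | Restricted, sham vs active | Subjects per arm | Power |
|---|---|---|---|---|---|
| 30% | 96.9% vs 98.8% | 11% | 36.5% vs 58.9% | 47 | 59% |
| 50% | 87.4% vs 94.9% | 32% | 36.5% vs 61.3% | 58 | 77% |
| 80% | 59.3% vs 82.1% | 80% | 31.8% vs 61.5% | 62 | 92% |
| 90% | 47.2% vs 75.9% | 92% | 31.7% vs 63.5% | 62 | 95% |
| 100% | 34.8% vs 68.8% | 97% | same | 62 | 97% |

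**No clearing at all (s = 0).** The share of subjects still scored as responders is P(Bin(4, 1 − q) ≥ 2): 92% at 30% prevalence, 69% at 50% and 18% at 80%.

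**Allowing new onset.** Let e be the chance that an initially absent symptom appears by 2 hours. Then x = (1 − q)(1 − e) + q·s. Take q = 0.4, where with no new onset power is 19% as written and 69% restricted.

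- e = 20% sham, 10% active: x = 0.60 vs 0.74, responders 82.1% vs 94.3%, power 56% as written.
- e = 40% sham, 20% active: x = 0.6 × 0.6 + 0.4 × 0.3 = 0.48 vs 0.6 × 0.8 + 0.4 × 0.5 = 0.68, responders 65.7% vs 90.0%, power 91% as written.

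The first case narrows the gap to the restricted version and the second reverses it.

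**The case against.** A reader might infer that the wording hides any device effect, or that both arms must sit near a ceiling. The documents do not support either. They give no symptom prevalence. At 80% to 90% the literal wording keeps 80% to 92% power under the assumptions above, and with no clearing at all only 18% of subjects would be responders at 80% prevalence. The three symptoms may also differ in prevalence, so the loss need not be the same for each.

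The strongest point on the other side is prevention. The device is meant to be used early, and the hypothesis (5.2) is that it aborts the attack. A symptom absent at onset may emerge by 2 hours, where it counts as a failure. The all-attack endpoint then captures something the restricted one discards, and if that effect is large the all-attack version can be the more powerful. This stands. It is why the all-attack analysis should be kept and why the power table is conditional.

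Secondary endpoint 1 is only a loose precedent: it varies the success rule by starting grade but excludes no attack and no subject. The restriction does both, and so leaves the full mITT set that section 7.7.4 names for performance. That is a real cost. Presence at start is recorded before any effect of treatment, however, so the restriction does not select on the 2-hour outcome.

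Sections 6.2, 7.8 and 9 refer to a separate statistical analysis plan, which could define the denominator. The text supplied does not.

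**Conclusion.** The gap in the definition is certain: no baseline-symptom condition appears anywhere in the text supplied, and the three endpoints do not separate resolution from absence or prevention. The direction is also clear for resolution, which is diluted. The size is not known. It rests on assumed clearing rates, independent attacks, no variation between subjects and no new onset. Under those assumptions the loss of power runs from 3 points at 90% prevalence (92% against 95%) to about 45 points or more at 50% and 30% (32% against 77%, 11% against 59%). New onset that the device prevents would reduce or reverse it.

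The consequences are confined to these three secondary endpoints. The primary endpoint, the sample size of 124 and type I error are untouched, and the dilution works against a false claim of benefit on resolution. This is a cheap improvement in clarity and, in many scenarios, in power. It is not a flaw that threatens the trial's main conclusion.

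**What to change.** In section 6.3.2, item 2, and the synopsis, define each endpoint as freedom from the symptom at 2 hours in at least half of the treated attacks in which that symptom was present at treatment start, as recorded on the existing start screen. Carry the same rule into sections 7.2.2 and 7.8.5. Leave a subject with no such attack out of that endpoint, and report the number of contributing subjects and attacks by arm. Keep the all-attack version as a supportive analysis, described as also capturing prevention of new onset. Settle this before any unblinded symptom data are seen, so that the denominator cannot look chosen from the results.

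No new data are needed. The costs are:

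- fewer subjects per symptom endpoint, about 47 per arm at 30% prevalence;
- a different subset for each symptom;
- some subjects classified on a single attack. Under the independence model their share is 4q(1 − q)³ / [1 − (1 − q)⁴], which is 0.4116/0.7599 = 54% of contributors at 30% prevalence and 4/15 = 27% at 50%.

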Participants will be instructed to activate the device at onset of a qualifying migraine attack and manually adjust stimulation intensity to a level within the pre-defined range where it is well perceived but not painful. A qualifying migraine attack shall be preceded by at least 48 hours of freedom from headache. Patients will be requested to refrain from use of rescue medications prior to and during the first two hours after treatment with the device, and if they can not comply with this, record their use of rescue medications (migraine specific drugs or other medications or therapies that may be used to treat pain, from a pre-specified list) in the mobile application.

Via the smartphone application, each participant will be asked to rate his/her migraine pain level three times using Pain Grades Scale (0 - no pain, 1- mild pain, 2- moderate pain, 3 – severe pain): (1) upon starting the treatment, (2) two hours after start of treatment, (3) 48 hours after start of attack. At the start of each treatment, participants will be also asked to provide time elapsed from start of migraine attack to start of the treatment. Participants will be also asked to provide feedback regarding their use of medication (migraine specific drugs or other medications or therapies that may be used to treat pain, from a pre-specified list), presence of nausea, photophobia and phonophobia, and treatment perception. After providing feedback at two hours

after start of treatment and in case of pain recurrence, participants will be allowed to re-treat the attack using Migra device.

Adverse events will be reported.

Duration of study participation for each patient will be up to three months, determined by one month of the roll-in stage followed treatment of four qualifying attacks over the course of two months (whichever is achieved first).

Post study questionnaire will include patient global impression of change [27], blinding and usability assessments.

Stage Three. This part will include open label extended treatment. Following the completion of the study by all subjects and the return of all study devices, subjects will be offered a 2-month period of using active device, at no cost.

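### Exploratory endpoint 2 can be overstated, because on the listed screens a relapse left untreated and gone by 48 hours cannot be told from no relapse

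*Combined protocol and SAP*

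**What the plan says.** Section 6.3.3 (and the Synopsis) lists as an exploratory endpoint the percentage of subjects who are pain-free at 2 hours without rescue medication and then meet one of two conditions. Either they "either have no relapse of pain within the subsequent 46 hours", or, if pain does return, "it disappears every time, after two hours, using the device, with no use of rescue medications".

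Pain is rated at treatment start, at 2 hours and at 48 hours. For the 48-hour rating, section 6.4.2.3 states "The screen shall provide for collection of the following data" and gives these fields:

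- a pain item, "Current migraine pain level in pain grade categories";
- a medication item, "Whether rescue medication was taken", with the drug name from a list;
- an optional text box, "Additional, free style feedback".

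Section 6.1 says that "in case of pain recurrence, participants will be allowed to re-treat the attack using Migra device". Section 6.4.3 adds that repeat treatments within 46 hours of the first are collected and analysed as exploratory data. It also says that rescue medication within 48 hours of the first treatment is a failure for sustained relief.

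Section 6.1 lists the last rating as "3) 48 hours after start of attack". The Synopsis (Study Procedures) and section 6.6.1 time it from the first treatment of the attack.

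Section 7.2.3 defines variables for 48-hour pain freedom and global impression of change, and section 7.8.5 analyses them. Neither mentions this composite endpoint.

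**The concern.** The endpoint depends on what happened over a 46-hour interval, but the listed ratings show pain only at its two ends. If pain came back and went away in between, and the subject used neither the device nor a drug, no listed field shows it. That subject fails the definition, but the data look like those of a subject whose pain never returned. If such subjects are counted as successes, the sustained pain-free rate is too high. No later analysis can reliably recover the lost information, so the question has to be asked while the attack is being recorded.

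**Working it through.** **Is the relapse recorded?** Take a subject who is pain-free at 2 hours without medication, and go through the ways in which pain can return by 48 hours.

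| Course after 2 hours | Status by definition | Trace in the listed data |
|---|---|---|
| No return of pain | Success | Pain 0 and no medication at 48 h |
| Returned, re-treated with device, pain 0 two hours later, no drug | Success | Repeat treatment and its 2 h screen |
| Returned, re-treated with device, pain above 0 two hours later | Failure | Repeat treatment and its 2 h screen |
| Returned, rescue medication taken | Failure | Medication items at 48 h |
| Returned, neither device nor drug, still present at 48 h | Failure | Pain above 0 at 48 h |
| Returned, neither device nor drug, gone by 48 h | Failure | Pain 0 and no medication at 48 h |

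The first and last rows leave the same record but have opposite status. Every other row can be identified. Rows two and three assume that the 2-hour screen also follows a repeat treatment. Section 6.4.2.2 ties that screen to the start of a treatment program without limiting it to the first, so this is a reasonable inference. Activation times are also logged (section 6.4.1).

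**How large could the error be?** The documents give no figure for the last row, so this is an illustration under stated assumptions.

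Overstatement = p × r × u, where

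- p is the 2-hour pain-free rate: 0.30 active and 0.10 sham, the planning rates in section 7.4;
- r is the share of 2-hour responders who relapse: assumed 0.10 to 0.40;
- u is the share of those relapses that are untreated and gone by 48 hours: assumed 0.25 to 0.50;
- r and u are taken as equal in both arms.

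Results:

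- Active, low: 0.30 × 0.10 × 0.25 = 0.0075, about 0.8 points. High: 0.30 × 0.40 × 0.50 = 0.060, or 6.0 points.
- Sham, low: 0.10 × 0.10 × 0.25 = 0.0025, about 0.3 points. High: 0.10 × 0.40 × 0.50 = 0.020, or 2.0 points.
- Difference between arms, low: 0.75 − 0.25 = 0.5 points. High: 6.0 − 2.0 = 4.0 points.

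With 62 subjects per arm, the active figures are 62 × 0.0075 ≈ 0.5 to 62 × 0.060 ≈ 3.7 subjects. The sham figures are 62 × 0.0025 ≈ 0.2 to 62 × 0.020 ≈ 1.2 subjects.

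The rates of 30% and 10% are planned for the primary endpoint, which requires success in at least half of treated attacks. Exploratory endpoint 2 states no such threshold, so these rates only stand in for its own.

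**When is the 48-hour rating taken?** The 2-hour rating is timed from the start of treatment, so the subsequent 46 hours end 2 + 46 = 48 hours after the start of treatment. The rescue rule in section 6.4.3 has the same end. A rating timed from the start of the attack, as in section 6.1, comes earlier by the delay from onset to treatment. Section 6.4.2.1 records that delay only in bands, the last of which is over 4 hours. In that band the rating would come more than 4 hours before the window closes, by an amount that the data cannot give exactly.

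**The case against.** The strongest case on the other side is that most relapses are handled correctly. A relapse cleared with the device is a success by the endpoint's own wording, a medicated relapse is asked about and fails, and pain still present at 48 hours is visible. This stands. A reader might infer that any relapse resolved by 48 hours is wrongly counted as sustained freedom, or that only device re-treatment reveals a relapse. The documents support neither reading.

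A reader might also infer that the plan scores the lost relapse as a success. It does not say so, because it gives no scoring rule for this endpoint. What can be said is that the listed fields do not separate the two cases.

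The screens may not be complete. Section 6.4.2 calls them an overview, and section 6.4 places the full list of case report forms in the Data Management Plan, which is not among the documents. A relapse item there cannot be excluded. Against this, section 6.4.2.3 is written at field level. Section 6.4.1 says that app-entered outcomes are used to calculate the endpoints and pass automatically into the case report forms. A form filled that way cannot hold an answer that the app did not request.

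Finally, it is tempting to say that the error favours active. On the difference scale, this requires the share of 2-hour responders with a lost relapse to be less than 0.30 / 0.10 = 3 times as high on sham as on active. That is plausible, but the documents do not establish it. With equal shares the ratio between arms does not change. The missing test for this endpoint is a minor matter, since section 7.8.1 already assigns tests for proportions.

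**Conclusion.** The point holds in a limited form. On the listed screens, one kind of relapse cannot be distinguished from no relapse: pain that returned, was treated with neither device nor medication, and had gone by 48 hours. The sustained pain-free rate can be overstated by the 2-hour rate times the share of responders with such a relapse. The documents give no value for that share. The illustrative 0.8–6.0 points on active and 0.3–2.0 on sham rest wholly on assumed shares, taken as equal in both arms, and on the primary endpoint's planning rates. The conflict over when the 48-hour rating is taken is real and bears on the same window. The endpoint is exploratory and lies outside the testing hierarchy in section 7.8.2.2, so neither the primary conclusion nor the success criterion is affected. This is a cheap improvement to make before data collection.

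**What to change.** 1. Add to the 48-hour screen: *Did the headache return between 2 and 48 hours after the start of the first treatment? (Y/N)* and, if yes, *Was any return not treated with the device? (Y/N)*. The second item is needed because the definition requires every relapse to clear with the device. A single yes/no cannot identify a subject with one re-treated and one untreated relapse.
2. Define the variable in section 7.2.3 from these two items, the 2-hour screen after each repeat treatment, and the rescue medication items. Count any return not treated with the device as a failure, as the definition implies. State how results from several attacks combine into one value per subject, since the definition gives no rule.
3. Reconcile the timing of the 48-hour rating in section 6.1 with the Synopsis and section 6.6.1, so that it matches the endpoint's post-treatment window and the rescue rule in section 6.4.3.

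The cost is up to two yes/no fields on an existing screen and a few sentences of text. The answers will carry some recall error over the interval.
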